5.1 Inclusion criteria

Participants eligible for inclusion in this study must meet **all** of the following criteria:

1. Written informed consent must be obtained and signed prior to participation in the study
2. Male or female patients with a diagnosis of CML-CP ≥ 18 years of age
3. Patients must meet all of the following laboratory values at the screening visit:
 - $< 15\%$ blasts in peripheral blood or bone marrow
 - $< 30\%$ blasts plus promyelocytes in peripheral blood or bone marrow
 - $< 20\%$ basophils in the peripheral blood
 - $\geq 50 \times 10^9/L$ ($\geq 50,000/mm^3$) platelets
 - Transient prior therapy related thrombocytopenia ($< 50,000/mm^3$ for ≤ 30 days prior to screening) is acceptable
 - No evidence of extramedullary leukemic involvement, with the exception of hepatosplenomegaly
4. Mutation Analysis testing performed at screening.
5. Prior treatment with a minimum of:
 - 2 prior ATP-site TKIs (i.e. imatinib, nilotinib, bosutinib, dasatinib or ponatinib) in case of absence of T315I mutation
 - 1 prior ATP site TKI (i.e. imatinib, nilotinib, bosutinib, dasatinib or ponatinib) in case of presence of T315I mutation
6. Failure (adapted from the 2020 ELN Recommendations) or intolerance to the most recent TKI therapy at the time of screening
 - Failure for CML-CP patients (CP at the time of initiation of last therapy) is defined as meeting at least one of the following criteria.
 - Three months after the initiation of therapy: $>10\%$ BCR-ABL1 on International Scale (IS) if confirmed within 1-3 months
 - Six months after the initiation of therapy: BCR-ABL1 ratio $> 10\%$ IS
 - Twelve months after initiation of therapy: BCR-ABL1 ratio $> 1\%$ IS
 - At any time after the initiation of therapy, loss of CHR, MR2
 - At any time after the initiation of therapy, the development of new BCR-ABL1 mutations which potentially cause resistance to current treatment
 - At any time 12 months after the initiation of therapy, BCR-ABL1 ratio $\geq 1\%$ IS or loss of MMR
 - At any time after the initiation of therapy, new clonal chromosome abnormalities in Ph+ cells: CCA/Ph+
 - Intolerance is defined as:
 - Non-hematologic intolerance: Patients with grade 3 or 4 toxicity while on therapy, or with persistent grade 2 toxicity, unresponsive to optimal management, including dose adjustments (unless dose reduction is not considered in the best interest of the patient if response is already suboptimal)

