|--------------------------------------|----------|--------------------|---|-------------------------------------|--------------|--------|--------|---------|---------|---------|---------|---------|---------|---------|---------|---------|---------|---------|--|
| | | | | Week 1 Day 1 | Week 2 Day 1 | Week 4 | Week 8 | Week 12 | Week 16 | Week 20 | Week 24 | Week 28 | Week 32 | Week 36 | Week 40 | Week 44 | Week 48 | Week 52 | |
| Prior/concomitant medications | D | 6.2 | X | Continuous | | | | | | | | | | | | | | | |
| Physical examination | S | 8.3 | X | X | | X | X | X | X | X | X | X | X | X | X | X | X | X | |
| Extramedullary Involvement | D | 8.3 | X | X | | X | X | X | X | X | X | X | X | X | X | X | X | X | |
| ECOG Performance status | D | 8.3 | X | X | | X | X | X | X | X | X | X | X | X | X | X | X | X | |
| Height | D | 8.3 | X | | | | | | | | | | | | | | | | |
| Weight | D | 8.3 | X | X | | | | X | | | X | | | X | | | X | | |
| Vital signs | D | 8.3 | X | X | X | X | X | X | X | X | X | X | X | X | X | X | X | | |
| Laboratory assessments | | | | | | | | | | | | | | | | | | | |
| Hematology | D | 8.3.1 | X | X | X | X | X | X | X | X | X | X | X | X | X | X | X | X | |
| Chemistry | D | 8.3.1 | X | X | X | X | X | X | X | X | X | X | X | X | X | X | X | | |
| Chemistry-Hemoglobin A1c | D | 8.3.1 | X | Week 12 and as clinically indicated | | | | | | | | | | | | | | | |
| Serum Pregnancy test (if applicable) | D | | X | | | X | X | X | X | X | X | X | X | X | X | X | X | | |
| Hepatitis markers | D | | X | | | | | | | | | | | | | | | | |

| Visit name | Category | Protocol Section 8 | Screening Phase | Treatment Phase | | | | | | | | | | | | | | |
|--|----------|--------------------|-----------------|-------------------------|--------------|--------|----------------|---------|---------|---------|---------|---------|---------|---------|---------|---------|---------|---------|
| | | | | Week 1 Day 1 | Week 2 Day 1 | Week 4 | Week 8 | Week 12 | Week 16 | Week 20 | Week 24 | Week 28 | Week 32 | Week 36 | Week 40 | Week 44 | Week 48 | Week 52 |
| Liver assessments | D | | | as clinically indicated | | | | | | | | | | | | | | |
| Efficacy assessments | | | | | | | | | | | | | | | | | | |
| Blood collection for BCR-ABL1 quantification by RQ-PCR | D | 8.4.1 | X | | | X | | X | | | | X | | | X | | | X |
| | | | | | | | | | | | | | | | | | | |
| Hematologic Response Assessment | D | 8.4.1 | | | | | | X | | | X | | | X | | | | X |

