**Table 2-2 Time windows for Hematologic response assessment**

Assessment	Target day of assessment	Time Interval
Week 12	85	Day 2 to day 127
Week 24	169	Day 128 to day 211
Week 36	253	Day 212 to day 295
Week 48	337	Day 296 to day 421
Week 72	505	Day 422 to day 589

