**Note:** Patient(s) who have reported for molecular response(s) at baseline will not be included in time to event analyses.

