### **Time to CHR, MR2, MR4, MR4.5 in 72 weeks of therapy**

Time to achieving a response level is defined as the time from the date of the first dose of study medication to the first documented achievement of a response level.

Time to achieve a specific response level will be analyzed using the Kaplan-Meier Product-Limit method. Patients who are known to be without achieving that response level will be censored at the last molecular & hematologic assessment.

The estimated cumulative incidence rates and 95% confidence intervals at 12, 24, 48 and 72 weeks will be presented. The cumulative incidence curve will be plotted. , if applicable. The analyses will be performed using FAS by cohort.

For patients in the FAS who have not experienced any molecular and/or hematologic response, the time will be censored as follows in the Kaplan-Meier analysis:

- If a patient does not achieve the specified response before the cut-off date for the analysis, censoring time will be the last molecular assessment (PCR) date on treatment prior to the cut-off date or the EoT visit, whichever comes first.
- If a patient discontinues study treatment prior to achieving a response for a reason other than disease progression or death, then the patient will be censored at the last molecular assessment (PCR) date on treatment prior to the cut-off date or the EoT visit, whichever comes first.

- If a patient discontinues study treatment prior to achieving a response due to progression or death, then the censoring time will be set to the longest follow-up time in the treatment group, that is, consider the response is impossible to reach.

In case no on-treatment response assessment was performed, the patient will be censored at day 1.

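### Time to CHR has no rule for patients already in CHR at entry, so some are counted as new responders at a date set by the visit schedule

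*SAP*

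**What the plan says.** - **Exclusion.** The Note in SAP 2.8.2 reads: "Patient(s) who have reported for molecular response(s) at baseline will not be included in time to event analyses". CHR is not mentioned.
- **Endpoint.** In the SAP section on time to CHR, MR2, MR4 and MR4.5, the clock starts at first dose and runs "to the first documented achievement of a response level". Analysis is by Kaplan-Meier with a cumulative incidence curve and estimates at 12, 24, 48 and 72 weeks. The population is given as: "The analyses will be performed using FAS by cohort".
- **Windows.** SAP Table 2-2 ("Time windows for Hematologic response assessment") starts at Week 12 with the interval "Day 2 to day 127" and target Day 85. It has no baseline row. Table 2-1, for molecular response, has one.
- **Schedule.** In Protocol Table 8-1 the row "Hematologic Response Assessment | D | 8.4.1 | | | | | | X" is blank from screening through Week 8, so the first scheduled response assessment is at Week 12. The blood counts that make up CHR are taken at screening, Week 1 Day 1, Week 2 Day 1 and every 4 weeks from Week 4 (Protocol Table 8-6). Extramedullary involvement is checked from screening (Table 8-4).
- **Definition.** CHR requires all its components to be present for at least 4 weeks (Protocol 8.4.2, SAP 2.8.2).
- **Eligibility.** Protocol 5.1, criterion 6, requires "Failure (adapted from the 2020 ELN Recommendations) or intolerance to the most recent TKI therapy at the time of screening". Intolerance, BCR-ABL1 above 1% at 12 months, loss of MMR or a new mutation each qualifies without loss of CHR.

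**The concern.** The SAP accepts that a patient already in molecular response has no informative time to that response, and removes such patients. The same reasoning applies to CHR but is not carried over. A patient who enters in CHR and stays in it meets the definition at the first point where the data allow it to be documented. That date comes from the schedule, and the treatment played no part in producing the response.

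The cumulative incidence curve then mixes responses gained on study with responses brought in at entry, and no baseline CHR status is derived that would let a reader separate them. The SAP also does not say whether CHR is dated from the scheduled response assessment or from the 4-weekly counts, so two programmers could get different medians from the same data. Duration of CHR starts at the same documented date and inherits the ambiguity.

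**Working it through.** **The plan's own figures.** The documents give no figure for time to CHR. The only design number used here is the cohort size. It is based on precision for an adverse-event rate and it reproduces: 1.96² × 0.18 × 0.82 / 0.12² = 39.4, rounded up to 40; 40 / 0.90 = 44.4, rounded up to 45.

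**Who is affected.** The Note can be read in two ways.

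1. It applies to the corresponding molecular endpoint only. Then every patient in CHR at entry stays in time to CHR.
2. It applies literally to all time-to-event analyses. Then patients in CHR with BCR-ABL1 ≤1% are already out, which sits badly with the stated FAS. Patients in CHR with BCR-ABL1 above 1% remain.

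On either reading, patients in CHR with BCR-ABL1 above 1% are counted.

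**When they are counted.** Dated from the scheduled response assessment, the event falls at Week 12, target Day 85. Dated from the 4-weekly counts, with the 4 weeks counted from Day 1, it falls at 1 + 28 = Day 29.

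**Effect on the Week 12 level.** Let p0 be the share in CHR at entry who remain in the analysis, and q the share of the others with CHR by Week 12. Both are assumptions. With no dropout:

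- reported incidence = p0 + (1 − p0) × q
- incidence among those who could respond = q
- part of the events carried in from entry = p0 / reported incidence

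With q = 0.30 and 45 patients:

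| p0 | Reported | After exclusion | Part carried in | Patients left |
|---|---|---|---|---|
| 0.20 | 0.20 + 0.80 × 0.30 = 0.44 | 0.30 | 45% | 36 |
| 0.40 | 0.40 + 0.60 × 0.30 = 0.58 | 0.30 | 69% | 27 |
| 0.60 | 0.60 + 0.40 × 0.30 = 0.72 | 0.30 | 83% | 18 |
| 0.80 | 0.80 + 0.20 × 0.30 = 0.86 | 0.30 | 93% | 9 |

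**Effect on the median, dated from the scheduled assessments.** Assume an exponential true time to CHR with median m weeks among patients not in CHR at entry. With the 4-week rule, documentation at Week 12 needs onset by Week 8, so q = 1 − 2^(−8/m).

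| m (weeks) | q | Reported at Week 12, p0 = 0.40 | Median, p0 = 0.40 | Median, no one in CHR at entry |
|---|---|---|---|---|
| 2 | 0.94 | 0.96 | Day 85 | Day 85 |
| 6 | 0.60 | 0.76 | Day 85 | Day 85 |
| 12 | 0.37 | 0.62 | Day 85 | Day 169 |
| 24 | 0.21 | 0.52 | Day 85 | Day 253 |

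For the last column: with m = 12, onset by Week 20 gives 1 − 2^(−20/12) = 0.69 at the Week 24 visit. With m = 24, the Week 24 value is 1 − 2^(−20/24) = 0.44 and the Week 36 value is 1 − 2^(−32/24) = 0.60.

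At p0 = 0.40 the median stays at Day 85 across a twelvefold range of true speed. At p0 = 0.20 it falls on Day 85 or Day 169, depending on m. Dated from the 4-weekly counts, p0 = 0.60 or 0.80 puts the median at Day 29, because more than half the patients have already been counted by then.

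**The case against.** - **The curve is not empty of information.** A reader might infer that it shows only the visit schedule and nothing about asciminib. The documents do not support that. Patients not in CHR at entry contribute real, interval-censored responses: at p0 = 0.40 the Week 12 level still falls from 0.96 to 0.52 as true response slows. The curve is a mixture.
- **Twelve weeks is one reading only.** A reader might also infer that every patient in CHR at entry gets a time of about 12 weeks. A single Week 12 visit cannot show 4 weeks' persistence, so earlier counts must be used in some way, the first window in Table 2-2 opens on Day 2, and unscheduled assessments are slotted too. Day 29 is as defensible as Day 85. This objection stands, and it exposes the missing dating rule.
- **The Note may already cover some patients.** Read literally, it removes those with BCR-ABL1 ≤1%. It does not reach those above 1%.
- **Baseline CHR cannot be fully confirmed.** Screening assessments fall within 21 days before Week 1 Day 1 (Protocol 8.1), which is shorter than the 4-week rule. After Week 4, physical examinations may be omitted except at Weeks 12, 24, 36, 48 and 72 (Table 8-4). Both facts stand and shape the fix.
- **Visit-driven dating is ordinary interval censoring.** True: excluding patients in CHR at entry does not remove it, as the last column of the median table shows.
- **The stakes are modest.** Safety is the primary objective, no hypothesis is tested, and the cohorts are not powered for comparison.

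**Conclusion.** The gap is real and limited in scope. Followed as written, the plan counts patients already in CHR at entry, at least those with BCR-ABL1 above 1%, as new CHR events on a schedule-driven date. This inflates the cumulative incidence of CHR and can fix its median at a visit date.

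The size depends on a share the documents do not give. With 30% of the other patients responding by Week 12, entry shares of 20% to 80% give reported values of 44% to 86% against 30%. On the Week 12 schedule, a share of 40% held the median at Day 85 for every true median tried, from 2 to 24 weeks. These figures assume no dropout and, for the medians, exponential response times.

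The point does not show an error in the molecular endpoints or in the CHR rate. It concerns descriptive secondary CHR endpoints, and the sponsor should correct it before the final analysis.

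**What to change.** In SAP 2.8.2 and Table 2-2:

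1. Add a baseline row to Table 2-2. Derive baseline CHR status from the component criteria, using the last hematology with differential and the last extramedullary check on or before first dose. Do not require 4 weeks' persistence before entry.
2. Extend the Note so that patients meeting these criteria at baseline are excluded from time to CHR. State that the molecular exclusion applies to the corresponding molecular endpoint.
3. State which data date CHR, and apply the rule consistently: either the 4-weekly hematology with the most recent available extramedullary examination, or the scheduled response assessment.

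Reporting the CHR rate by baseline CHR status would be a useful but optional addition.

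**Cost.** SAP wording and programming on data already collected; no new visit or sample. Time to CHR rests on fewer patients: at p0 = 0.40 a cohort of 45 falls to 27, and as a guide the exact 95% interval at Week 12 goes from 0.42–0.72 (26 of 45) to 0.14–0.50 (8 of 27). Baseline CHR becomes a component-based approximation of the protocol definition, which the report should say.

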### **Time to CHR, MR2, MR4, MR4.5 in 72 weeks of therapy**

Time to achieving a response level is defined as the time from the date of the first dose of study medication to the first documented achievement of a response level.

Time to achieve a specific response level will be analyzed using the Kaplan-Meier Product-Limit method. Patients who are known to be without achieving that response level will be censored at the last molecular & hematologic assessment.

The estimated cumulative incidence rates and 95% confidence intervals at 12, 24, 48 and 72 weeks will be presented. The cumulative incidence curve will be plotted. , if applicable. The analyses will be performed using FAS by cohort.

For patients in the FAS who have not experienced any molecular and/or hematologic response, the time will be censored as follows in the Kaplan-Meier analysis:

- If a patient does not achieve the specified response before the cut-off date for the analysis, censoring time will be the last molecular assessment (PCR) date on treatment prior to the cut-off date or the EoT visit, whichever comes first.
- If a patient discontinues study treatment prior to achieving a response for a reason other than disease progression or death, then the patient will be censored at the last molecular assessment (PCR) date on treatment prior to the cut-off date or the EoT visit, whichever comes first.

- If a patient discontinues study treatment prior to achieving a response due to progression or death, then the censoring time will be set to the longest follow-up time in the treatment group, that is, consider the response is impossible to reach.

In case no on-treatment response assessment was performed, the patient will be censored at day 1.

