On cohort C, patients harboring the T315I mutation will be treated on the dose of 200 mg twice daily (BID). The higher dose required for that patient population is related to its required concentration to attain optimal blockade of the kinase activity. Patients will continue therapy until disease progression, unacceptable toxicity or elective treatment discontinuation.

4 Rationale

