8.1.3 Treatment Period

All patients will be given the opportunity to receive study treatment until the end of study treatment period as defined in [Section 6.1](#).

During the treatment phase, the patients will receive either asciminib treatment 40 mg BID, 80 mg QD or 200 mg (if T315I Mutation).

The dose can be modified, if required from the perspective of tolerance, following the guidance in [Section 6.5](#). Treatment will be administered until patient experiences treatment failure, unacceptable toxicity, disease progression, death, lost to follow-up and/or treatment is discontinued at the discretion of the investigator or withdrawal of consent.

The patients are advised to adhere to the food restrictions during the treatment (fasting status regarding study treatment administration, avoidance of prohibited concomitant medication).

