9.1 Discontinuation and completion

9.1.1 Study treatment discontinuation and study discontinuation

Discontinuation of study treatment for a subject occurs when study treatment is stopped earlier than the protocol planned duration and can be initiated by either the subject or the investigator.

The investigator must discontinue study treatment for a given subject if, he/she believes that continuation would negatively impact the subject's well-being.

Patients who discontinue the study treatment for an adverse event suspected to be related to study drug or an abnormal laboratory value suspected to be related to study drug must be followed as described in [Section 8](#)

Patients may also be discontinued from the study treatment if any of the following occurs:

- discovery of patient ineligibility
- errors in treatment compliance [study treatment, other prescribed or non-prescribed medications]
- missed/unscheduled/off schedule/incomplete/incorrect assessments
- major protocol deviation
- use of prohibited treatment refer to [Section 15-Appendices](#)
- any other protocol deviation that results in a significant risk to the patient's safety

In addition to the general discontinuation criteria, the following study specific criteria will also require discontinuation of study treatment:

- In the event of detection of new T315I mutations during the study, the patient **must** be discontinued from the study treatment. The Novartis Managed Access Program (MAP) ABL001A02401M Cohort will be available for those patients without a reasonable alternative options if treating physician and patient still choose to pursue treatment with Asciminib.
- In the event of a pregnancy during study, if a patient wants to pursue the pregnancy then patient **must** be discontinued from the study treatment. However, in the event of a spontaneous miscarriage or in the event of elective abortion, the patient is permitted to continue study treatment.
- In the event of treatment failure the patient must be discontinued from the study treatment. The following events will constitute 'treatment failure', defining failure of a third line treatment:
 - No CHR at three months after initiation of therapy or thereafter
 - BCR-ABL1 ratio > 10% IS at 24 weeks after initiation of therapy or thereafter
 - BCR-ABL1 ratio > 1% IS at 48 weeks after initiation of therapy or thereafter
 - Loss of CHR, MR2 at any time after initiation of therapy

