- Detection of new BCR-ABL1 mutations which potentially cause resistance to study treatment (asciminib) at any time after initiation of therapy
- Confirmed loss of MMR in 2 consecutive tests ([Section 8.5](#)) (BCR-ABL1 > 0.1%)
- In the event of disease progression the patient must be discontinued from the study treatment. The following events are considered disease progression.
 - CML-related death (any death during treatment or follow-up if the principal cause of death is marked as “study indication” in the eCRF by the investigator, or if the death occurred subsequent to documented progression to AP/BC and the cause of death is reported as “unknown” or not reported by the investigator).
 - Accelerated phase (AP) as defined by any of the following:
 - $\geq 15\%$ blasts in the peripheral blood or bone marrow aspirate, but $< 30\%$ blasts in the peripheral blood or bone marrow aspirate
 - $\geq 30\%$ blasts plus promyelocytes in peripheral blood or bone marrow aspirate
 - $\geq 20\%$ basophils in the peripheral blood
 - Thrombocytopenia ($< 100 \times 10^9/L$) that is unrelated to therapy
 - Blast crisis (BC) as defined by any of the following:
 - $\geq 30\%$ blasts in peripheral blood or bone marrow aspirate

If discontinuation of study treatment occurs, the investigator should make a reasonable effort to understand the primary reason for the subject’s premature discontinuation of study treatment and record this information.

Subjects who discontinue study treatment or who decide they do not wish to participate in the study further should NOT be considered withdrawn from the study UNLESS they withdraw their consent (see withdraw of informed consent section.). Where possible, they should return for the assessments indicated in the assessment schedule. If they fail to return for these assessments for unknown reasons, every effort (e.g. telephone, e-mail, letter) should be made to contact the subject/pre-designated contact as specified in the lost to follow-up section. This contact should preferably be done according to the study visit schedule.

If the subject cannot or is unwilling to attend any visit(s), the site staff should maintain regular telephone contact with the subject, or with a person pre-designated by the subject. This telephone contact should preferably be done according to the study visit schedule.

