**Figure 1-1 Schematic of study design**

For patients without T315I mutation, patients will be selected randomly between Cohort A, where patients will be given asciminib at 40 mg twice daily (BID) and Cohort B, where patients will receive asciminib at 80 mg daily (QD) to minimize selection bias. In Cohort C, patients harboring the T315I mutation will be enrolled and treated on the dose of 200 mg twice daily (BID). The higher dose required for that patient population is related to its required concentration to attain optimal blockade of the kinase activity. Patients will continue therapy until disease progression, unacceptable toxicity, or elective treatment discontinuation.

AEs, SAEs, and laboratory evaluation for 24 weeks is the primary endpoint in this study. AEs, SAEs and laboratory evaluation for Cohort A, B and Cohort C, during 48, 72 weeks is the secondary safety endpoint.

The primary analysis will be performed after all patients have been followed for at least 24 weeks or have discontinued study earlier. The end of study medication analysis will be performed after all patients have been followed for at least 72 weeks or have discontinued study earlier. The PFS/OS update analysis will be performed during 24, 48 and 72 weeks of the last patient received the first study dose.

No formal interim efficacy analysis is planned in this study. As the primary time point is by 24 weeks, the primary analysis will be an interim analysis performed when the last patient completes 24 weeks of treatment or discontinues early. As appropriate, annual interim analyses may be planned for publication or any regulatory purpose. Only summary statistics will be provided.

Final Analysis will be performed when the last patient completes 72 weeks of treatment or discontinues early.

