### **2.8.3 Handling of missing values/censoring/discontinuations**

#### **MMR rates by specific time points:**

Patients without any documented response for which an evaluable response assessment was never provided will be considered as non-responders for the period of time up to that time point.

**Molecular response category by specific time points:** The category “Missing” will be assigned to patients for whom an evaluable response assessment was never provided.

**Time to MMR:** For patients in the FAS who have not experienced any MMR, the time will be censored as follows in the Kaplan-Meier analysis:

If a patient does not achieve the specified response before the cut-off date for the analysis, censoring time will be the last molecular assessment (PCR) date on treatment prior to the cut-off date or the EoT visit, whichever comes first.

If a patient discontinues study treatment prior to achieving a response for a reason other than disease progression or death, then the patient will be censored at the last molecular assessment (PCR) date on treatment prior to the cut-off date or the EoT visit, whichever comes first.

If a patient discontinues study treatment prior to achieving a response due to progression or death, then the censoring time will be set to the longest follow-up time in the treatment group, that is, consider the response is impossible to reach.

In case no on-treatment response assessment was performed, the patient will be censored at day 1.

[figure not shown]
**Duration of MMR:** For patients who have not experienced any event (loss of MMR, progression to AP/BC, or CML-related death), the duration will be censored at the last molecular assessment (PCR) date on treatment.

[figure not shown]
**PFS:** For patients who have not experienced protocol defined event (disease progression to AP/BC or death from any cause), the patients will be censored at the date of last study assessment (PCR, cytogenetic, hematologic or extramedullary) before the cut-off date.

**OS:** Patients who are alive at the time of the analysis data cutoff date will be censored at the date of last contact (see Section 2.1.1) before the cut-off date.

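### Non-responders taken off treatment for failure are censored, so the Kaplan-Meier cumulative incidence of molecular response leans upward at Weeks 48 and 72

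*SAP*

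**What the plan says.** **Time to response.** SAP 2.8.2 (time to CHR, MR2, MR4 and MR4.5) and SAP 2.8.3 (time to MMR) carry the same rules. For a patient who stops before responding because of progression or death, "then the censoring time will be set to the longest follow-up time in the treatment group", on the ground that response can no longer be reached. For a patient who stops "for a reason other than disease progression or death, then the patient will be censored at the last molecular assessment (PCR) date on treatment" or at the end-of-treatment visit, whichever is first. SAP 2.8.2 then presents cumulative incidence with 95% confidence intervals at Weeks 12, 24, 48 and 72.

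**Stopping treatment.** Protocol 9.1.1 states: "In the event of treatment failure the patient must be discontinued from the study treatment". Its failure criteria include no CHR at three months, BCR-ABL1 above 10% from 24 weeks, and "BCR-ABL1 ratio > 1% IS at 48 weeks after initiation of therapy or thereafter". A separate item reads "In the event of disease progression the patient must be discontinued from the study treatment", with progression defined as accelerated phase, blast crisis or CML-related death. Protocol 8.1.3 also lists the two apart: "Treatment will be administered until patient experiences treatment failure, unacceptable toxicity, disease progression, death".

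**Response rates.** The rate paragraph of SAP 2.8.2 counts a patient who stops for any reason without MR2, MMR, MR4 or MR4.5 as a non-responder for that level.

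**The concern.** A patient above 10% or 1% on the International Scale is at least 100-fold or 10-fold above the MMR threshold of 0.1%. Protocol 9.1.1 removes such patients because of that level. The SAP then censors them, and Kaplan-Meier gives them the later response probability of the patients who were doing well enough to stay. The censoring is informative.

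One minus Kaplan-Meier with a competing event censored is never below the cumulative incidence actually achieved on treatment. It is strictly above once a single failure is censored before a later response. So the direction needs no assumed rate; only the size does. At stake are reported efficacy figures that readers will take as the share of patients who responded on treatment.

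**Working it through.** The plan gives no expected Kaplan-Meier response to reproduce. Its one design calculation, the sample size, concerns adverse-event incidence. It reproduces (1.96² × 0.18 × 0.82 / 0.12² = 39.4, so 40; 40 / 0.9 = 44.4, so 45) and has no bearing here.

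**Inputs**
- r24 = 0.32 and r48 = 0.44: MMR at 6 and 12 months (Protocol Summary; Protocol 4.1), taken as Weeks 24 and 48.
- r72 = 0.48: assumed.
- f24 and f48: shares of all patients removed as non-responders for failure just after Weeks 24 and 48. Not in the documents; varied.
- No other discontinuations.

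**Formulas** (events before censorings at ties; responses at intermediate visits cancel)
- S48 = (1 − r24) × (1 − r48 − f24) / (1 − r24 − f24)
- S72 = S48 × (1 − r72 − f24 − f48) / (1 − r48 − f24 − f48)
- Reported value = 1 − S. With f24 = f48 = 0 this returns 44% and 48%, the on-treatment values.

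**MMR, all failures censored**

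| f24 + f48 | S48 | Week 48 | S72 | Week 72 | Shift (points) |
|---|---|---|---|---|---|
| 3% + 3% | 0.68 × 0.53/0.65 = 0.554 | 44.6% | 0.554 × 0.46/0.50 = 0.510 | 49.0% | +0.6 / +1.0 |
| 5% + 5% | 0.68 × 0.51/0.63 = 0.550 | 45.0% | 0.550 × 0.42/0.46 = 0.503 | 49.7% | +1.0 / +1.7 |
| 15% + 20% | 0.68 × 0.41/0.53 = 0.526 | 47.4% | 0.526 × 0.17/0.21 = 0.426 | 57.4% | +3.4 / +9.4 |

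The last row is an extreme: 35 of the 56 points still without MMR at Week 48 have been removed.

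**Coding of the stopping reason.** Failures recorded as progression stay in the risk set, so only the rest enter f24 and f48. If half are so recorded, the shifts are +0.3 / +0.5 (3% + 3%) to +1.5 / +3.2 (15% + 20%). If all are, the shift is zero.

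**Sensitivity, 3% + 3% to 15% + 20%, all censored**
- r72 of 0.46: +0.8 to +6.4 at Week 72. r72 of 0.50: +1.2 to +12.4.
- T315I rates of 25% and 28% (Protocol 1.1.2.2), assumed 30% at Week 72: +0.1 to +0.8 at Week 48 and +0.3 to +2.6 at Week 72.
- MR4, assumed 10%, 20% and 25%: +0.3 to +2.0 and +0.7 to +5.7.
- MR2, assumed 45% at Week 24 and 54% at Week 48, with 3% to 15% removed after Week 24: +0.5 to +3.4 at Week 48. The 54% is the CCyR figure in Protocol 1.1.2.2, which has no time point; Protocol 8.4.1 equates CCyR with a level below 1%. The 48-week criterion then removes every remaining MR2 non-responder, so the excess carries unchanged to Week 72.

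**Indirect anchor.** Protocol 1.1.2.2 reports 76 discontinuations among 239 patients: 38 for progression, 15 for adverse events, 3 deaths. The remaining 20 (8.4%), split evenly over the two time points, give +0.8 / +1.4. This residual is not a failure rate: it may include withdrawals and losses, that study included ALL patients, and its stopping rules are not given.

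**What moving only treatment failures would leave.** The 15 adverse-event stops (6.3%), split evenly and all taken as non-responders, give 44.6% and 49.0%, that is +0.6 / +1.0 still in place.

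**Other time points.** The three-month CHR criterion can remove non-responders before Week 24, so that value can shift slightly (not modelled). Week 12 is essentially unaffected.

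**The case against.** The strongest reply is that the plan already gives the wanted quantity. The SAP 2.8.2 rates use any-reason non-response with exact intervals at the same weeks, and no hypothesis is tested. The time-to-response rule is also stricter than Protocol 12.5.2.2, which censors every non-achiever at the last adequate assessment. All of this is true and limits the consequence. It does not correct the Kaplan-Meier figures, which are reported separately as cumulative incidence.

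Second, the size rests on assumed failure rates and on an eCRF coding that is not shown. That stands. SAP 2.3.4 shows that a primary reason is collected, not whether treatment failure is a category. The censoring bullets say progression without the AP/BC qualifier that the SAP uses for duration of response and PFS. But Protocol 9.1.1 separates the two, and an estimate should not depend on site labelling.

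Third, the lists of stopping reasons differ. SAP 1.1 says "Patients will continue therapy until disease progression, unacceptable toxicity, or elective treatment discontinuation" and Protocol 3 says "Patients will continue therapy until disease progression, unacceptable toxicity or elective treatment discontinuation"; the Protocol Summary and Protocol 6.1.6 also omit treatment failure. These can be read as summaries beside the operative text in 8.1.3 and 9.1.1, and they do not show how sites code the reason.

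Fourth, a reader might infer that reclassifying treatment failures alone is enough. It is not: adverse-event and other stops also end the chance of response on study treatment.

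**Conclusion.** The point holds as a bias of known direction and unknown size. As an estimate of response achieved on study treatment, the Kaplan-Meier cumulative incidence of MMR, MR4 and MR4.5 is too high at Weeks 48 and 72, and that of MR2 at Week 48 with the same excess at Week 72. Failure rates of 3% to 5% at each time point put the MMR shift at about 0.6 to 1.0 points at Week 48 and 1.0 to 1.7 at Week 72. For scale, the exact 95% interval for 20 of 45 is 30% to 60%. The issue is minor to moderate.

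Three stronger readings are not supported:
- That the reported response rates are inflated. They are not; discontinued non-responders already count against them.
- That the overstatement is large. The 9.4 points need an extreme failure rate that the documents do not give, an assumed Week 72 value, and no failure recorded as progression.
- That the curves must lie above the response rates. The note in SAP 2.8.2 excludes baseline responders from the time-to-event analyses only, so the two need not line up.

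**What to change.** In SAP 2.8.2 and 2.8.3, state that the target is response achieved on study treatment. Estimate it by Aalen-Johansen cumulative incidence, with discontinuation of study treatment before response, for any reason, as the competing event. Censor only patients still on treatment without response at the cut-off. The existing longest-follow-up rule, extended to all such discontinuations, does the same job: the two agree when every patient has 72 weeks of potential follow-up, as at the final analysis. This matches the any-reason rule already used for the molecular response rates and needs no reclassification of recorded stopping reasons. Baseline responders stay excluded; say so beside the curves and point to the rates for the response proportions.

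Record the departure from Protocol 12.5.2.2 in SAP Section 4, which currently reports no change although the progression-and-death rule already departs from it. Date the change, because the study is open-label and the SAP history places its last amendment before an interim lock that follows the primary analysis.

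The differing lists of stopping reasons (Protocol Summary, Protocol 3 and 6.1.6, and SAP 1.1 against Protocol 8.1.3 and 9.1.1) should be reconciled; this review does not say which applies.

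Cost: a short edit in two SAP sections and a reprogrammed estimate from data already collected. The reported cumulative response becomes slightly less favourable.
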